#### FU 4 at WK52: all patients (Day 364 ± 7 days): all patients

All reasonable efforts should be made to achieve on-site visits being conducted. Should this not be possible, a home visit by a study team shall be performed, or, if this is again not possible, telephonic visits will be conducted to obtain health status, information on TB treatment outcome and eventual re-treatment, and pregnancy status if the patient is a woman of childbearing potential.

Administrative & regulatory		• N/A
Clinical		
 
Physical examination, vital signs at FU 1 (WK18); at FU 2-4 (WK26, WK38, WK52) symptom orientated physical examination only or to follow up on (S)AEs
 
Neurological examination/vision testing at FU 1 (WK18); at FU 2-4 (WK26, WK38, WK52) symptom orientated neurological examination only or to follow up on (S)AEs
 
Concomitant medication
 
Adverse events
 

Laboratory	Blood	
 
Safety laboratory (blood sample of 9.5mL) at FU 1 (WK18)
 
Serum pregnancy test (blood sample of 7.5mL), if female of childbearing potential at FU 1 (WK18) only
 

	Urine	Urinalysis at FU 1 (WK18) only
Microbiology		
 
Spot sputum (2 sample)
 
Ziehl-Neelsen smear from concentrated sample
 
Culture in BD MGIT liquid media
 
Culture on LJ solid media
 
Analysis by MBLA and/or sputum LAM, if capacity/budget permits
 

Study drugs		• Standard of care TB treatment from government health system outside of the study, if patient did not meet the definition for sustained culture conversion by week 08.

Protocol No: PanACEA - DECODE – 01/ LCB01-0371-20-2-02 Protocol Version No: V2.1, dated 08 September 2021

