#### 11.4 Assessments when Recurrence is Suspected

During follow-up, patients who are experiencing complaints, or have laboratory events suggesting a recurrence of disease, will be evaluated in a standardized manner that has been described for the TBTC study 31 [58].

Triggers for the assessment will be the following events:

- A positive culture confirmed as M. tuberculosis from a sputum specimen collected at or after the WK16 visit
- Worsening signs and/or symptoms consistent with tuberculosis at or after WK16
- The site investigator is considering an extension of tuberculosis therapy beyond 16 weeks

The following procedures shall be conducted:

- Assessment of symptoms
- Review interval medical history
- Weight, vital signs and physical examination
- Obtain 3 sputum specimens for smear and MGIT plus LJ culture, 2 specimens at least 4h apart. If M. tuberculosis is isolated, the isolate is to be stored frozen.
- Chest radiograph
- Review participant's contact information, and update if indicated
- Contact sponsor medical expert to review procedures, results and decide on management

The outcome of this assessment will be twofold:

- to define whether the patient will have met the endpoint of "relapse", conditional on a matching of baseline and recurrence isolate, if available;
- to transfer the patient to the government TB treatment programme to receive treatment for recurrent disease

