11.2. Relapse

An important secondary outcome is the proportion of participants who suffer relapse among those completing 16 weeks of therapy, achieve early culture conversion to negative in liquid media if there is a culture negative timepoint at two consecutive visits, the first of which is at or before week 08, without an intervening culture positive timepoint, and terminating therapy.

All participants will be classified as follows:

- Not achieved culture conversion to negative before or at week 8 after randomization (based on the analysis visit window).
 These participants will not end treatment at week 16 according to the protocol and therefore are not included in the relapse analysis.
- Relapse defined as having two consecutive culture positive timepoints without an intervening culture negative timepoint where the first occurs after Week 16 after randomization (based on the analysis visit window) and the recurrence strain of MTb is shown to be the same as that at baseline. If strain typing results are missing or inconclusive, a recurrence will be considered a relapse (rather than a reinfection).
- Reinfection defined as having two consecutive culture positive timepoints without an intervening culture negative timepoint where the first occurs after Week 16 after randomization (based on the analysis visit window) and the recurrence strain of MTb is shown to be different from that at baseline.
- Died at any point during the study
- Culture positive timepoint when last seen (not meeting criteria for other outcomes above)
- Culture negative timepoint when last seen (not meeting criteria for other outcomes above)

Outcomes will be tabulated by treatment arm among all in the ITT analysis population and among those in the AA analysis population.

A sensitivity analysis will be conducted repeating this relapse analysis using the second definition of time to culture conversion described below under the latter part of section 11.4.

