11.3. Time to recurrent TB and relapse

Time to recurrent TB will be defined as time from randomization to first culture positive timepoint that leads to a classification of relapse or reinfection. Participants without reinfection or relapse will be censored at time of last culture result. Time to relapse will be defined in the same way, except considering only relapses (and not reinfections) as events.

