12.6. Visit Windows

For timing of data items, the time is based on actual visit dates where data was collected (e.g. blood sample, sputum sample, data recorded) rather than scheduled visit name or date. The time from randomization is calculated as the difference between visit date and randomization date + 1 (so that data collected on the day of randomization is on day = 1).

Any visit, scheduled or unscheduled, that falls into the analysis window below will be assigned to that visit for the purpose of analysis. If two visits fall within the same interval, the one closet to the target date will be used for the analyses by visit, so that there is only one unique visit for each patient and analysis time-point. These visit windows relate to analyses of tabulations of data by visit.

Visit	Target Date: Days after Treatment	nt Analysis Window
	Allocation (wk*7+1)	
Baseline	1	Date of screening consent-3
Week 01	7	4-10
Week 02	14	11-17
Week 03	21	18-24
Week 04	28	25-31
Week 05	35	32-38
Week 06	42	39-45
Week 07	49	46-52
Week 08	56	53-59

Week 09	63	60-66
Week 10	70	67-73
Week 11	77	74-80
Week 12	84	81-87
Week 13	91	88-94
Week 14	98	95-101
Week 15	105	102-108
Week 16	112	109-121
Week 18	126	122-154
Week 26	182	155-210
Week 38	266	211-313
Week 52	364	314-no upper bound

13. Safety Analysis

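### SAP 11.2 counts relapse only from two consecutive positive timepoints and does not use the Protocol 11.4 assessment, so a recurrence diagnosed on one positive timepoint and retreated can be recorded as event-free

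*SAP*

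**What the plan says.** Protocol 9.2.2 and SAP 5.2.2 define relapse as recurrent disease with the baseline strain within 12 months of randomisation, among patients who converted early and completed 16 weeks of therapy. Neither asks for two positive timepoints.

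Protocol 11.4 sets out a standardised assessment for suspected recurrence. One positive culture at or after WK16 triggers it, and so do worsening symptoms alone. Three sputum specimens are taken and the sponsor medical expert is consulted. The assessment has two stated outcomes: to establish whether the relapse endpoint is met, subject to matching isolates where available, and "to transfer the patient to the government TB treatment programme to receive treatment for recurrent disease".

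SAP 11.2 works from cultures only: "Relapse defined as having two consecutive culture positive timepoints without an intervening culture negative timepoint where the first occurs after Week 16". Reinfection has the same rule with a different strain. Survivors who do not meet it go to "Culture positive timepoint when last seen (not meeting criteria for other outcomes above" or "Culture negative timepoint when last seen (not meeting criteria for other outcomes above". SAP 11.3 adds: "Participants without reinfection or relapse will be censored at time of last culture result".

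SAP 12.6 assigns unscheduled as well as scheduled visits to analysis windows and then says "If two visits fall within the same interval, the one closet to the target date will be used for the analyses by visit". The WK52 window is "314-no upper bound". The section ends by tying the windows to by-visit tabulations. SAP 11.2, however, refers to the analysis visit window when it fixes the Week 8 and Week 16 cut-offs.

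**The concern.** The protocol gives the relapse decision to a clinical and microbiological assessment. The SAP replaces that decision with a culture-count rule and has no category for a patient whom the assessment has diagnosed and referred. After referral, later cultures are taken on or after retreatment and may be negative, so the second positive may never come.

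The SAP itself rates relapse as an important secondary outcome. It bears on whether stopping at 16 weeks was adequate. The error runs one way: a diagnosed recurrence can move into a culture-negative row and become a censored observation. That sits badly with the SAP's own cautious choice to count missing or inconclusive strain typing as relapse.

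**Working it through.** No planned figure needs reproducing here; the point concerns a definition. I traced one patient through the rules, then checked what the window rule would do.

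**1. A patient who is missed however 12.6 is read**

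Inputs: SAP 11.1 (a timepoint is a visit, and one positive culture makes it positive); Protocol 11.4 (symptoms alone can trigger assessment); Protocol synopsis (referral follows a diagnosis of recurrence); Protocol 10.5.3 (FU4 is for all patients); SAP 11.2 and 11.3. Assumptions: the three specimens come from one visit, and the later culture is negative.

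| Day | Event | Timepoint |
|---|---|---|
| 126 | WK18 visit | negative |
| 160 | symptoms, 11.4 visit, diagnosis, referral | positive |
| 364 | WK52 visit after retreatment | negative |

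The longest run of positives is 1 and the rule needs 2. The patient is classed as culture negative at last contact. Under SAP 11.3 the patient is censored at day 364 instead of having an event at day 160, which credits 364 − 160 = 204 days of event-free time after the diagnosis. If the next culture were still positive, the relapse would be counted. The documents do not say whether a referred patient still attends WK26 and WK38; negative cultures there would not change the result.

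**2. What window thinning would do, if applied to relapse**

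A confirmatory visit survives as a separate timepoint only if it reaches the next window. Required gap = first day of next window − day of first positive.

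| First positive | Window (days) | Gap, on-time visit | Gap across visit tolerance |
|---|---|---|---|
| WK18 (126 ± 4) | 122–154 | 155 − 126 = 29 | 155 − 130 = 25 to 155 − 122 = 33 |
| WK26 (182 ± 7) | 155–210 | 211 − 182 = 29 | 211 − 189 = 22 to 211 − 175 = 36 |
| WK38 (266 ± 7) | 211–313 | 314 − 266 = 48 | 314 − 273 = 41 to 314 − 259 = 55 |
| WK52 (364 ± 7) | from 314, open-ended | none exists | none exists |

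With a shorter gap, only one of the two positive visits is kept. With a longer gap, the confirmatory visit competes with the next scheduled visit and loses if that visit is nearer its target. In the example above, an attended WK26 visit on day 182 is 0 days from target and the day-160 visit is 22 days away, so even the single positive would be dropped. A first positive at WK52 could never be paired and would end in the culture-positive row.

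The documents give no relapse timing. Let w be the share of relapses first positive at WK52, and q the chance that the next scheduled visit is still positive. Assume that visit is attended and the confirmatory visit is dropped. The share counted is then (1 − w) × q:

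- w = 0.25, q = 0.5: 0.75 × 0.5 = 37.5%
- w = 0.5, q = 0.5: 0.5 × 0.5 = 25%
- across all w and q: 0% to 100%

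This range shows only that no frequency can be derived. Without thinning, a positive 11.4 visit after a positive scheduled visit completes the pair, also after WK52.

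**3. Weight of one patient**

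With the planned 15 per arm, one reclassified patient moves an arm's proportion by at least 1/15 = 6.7 percentage points. The endpoint's denominator is limited to early converters who complete 16 weeks, so the shift may be larger. If 12 patients stopped (an assumption), it would be 1/12 = 8.3 points, for example 2/12 = 16.7% falling to 1/12 = 8.3%.

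**The case against.** A reader might infer that patients are retreated straight after their first positive, so that a second positive is almost never obtained. The documents do not support that. Referral depends on a diagnosis reached through the 11.4 assessment, which collects three further specimens. When a positive culture is the trigger, the assessment follows the result and so falls at a later visit. It can supply the second positive, including after WK52.

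A reader might also infer that SAP 12.6 definitely discards the confirmatory visit. That is only one reading. The section limits the windows to by-visit tabulations, and relapse is a per-participant classification. SAP 11.2's mention of the window concerns the cut-offs. The gaps in the table above, and the conclusion that a first positive at WK52 can never qualify, hold only under that reading.

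Four further points are fair:

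- Asking for confirmation is defensible, because SAP 11.1 calls a timepoint positive on one culture, even one reported as MTB with contamination.
- The endpoint is secondary and tabulated by arm, and Table 2.10 shows unconfirmed positives at last visit in their own row. The SAP does not label the culture-negative row favourable.
- Protocol 11.4 does not state that the three specimens come from one visit.
- Telephone follow-up at FU4 ("telephonic visits will be conducted to obtain health status, information on TB treatment outcome and eventual re-treatment") may reveal retreatment, but it yields no isolate, so such a patient is not clearly a missed relapse.

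These points narrow the concern but do not remove it. A patient with one positive timepoint, an 11.4 diagnosis, referral and a later negative culture still has no route to relapse, and Table 2.10 would not show that the patient had been diagnosed.

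**Conclusion.** The gap is real and does not depend on how 12.6 is read. SAP 11.2 leaves out the assessment that the protocol uses to settle the endpoint, and SAP 11.3 censors a diagnosed, retreated recurrence that lacks a second consecutive positive. The bias is towards too few relapses. This rests on such patients occurring and on their later cultures being negative; the documents support no estimate of how many. Each one is worth at least 6.7 percentage points in an arm of 15.

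The window question is a separate ambiguity. Two programmers could derive different relapse counts from the same data, and under the thinning reading the loss could be large. Because the endpoint is secondary and the primary endpoints are unaffected, this is a should-fix, not a must-fix.

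**What to change.** Amend SAP 11.2 and 11.3 as follows:

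- (a) State that the one-visit-per-window rule in 12.6 does not apply to relapse or recurrence, and that every unscheduled 11.4 visit counts as its own timepoint.
- (b) Also classify as recurrence a patient with at least one MTB-positive timepoint after Week 16 who is then diagnosed with recurrent disease under Protocol 11.4 and referred for TB retreatment. Date the event at that first positive, and let strain typing split relapse from reinfection as already planned.
- (c) Report the strict two-timepoint definition as a sensitivity analysis. Show retreatment without any positive culture in a separate row or a sensitivity analysis, not as relapse.

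Retreatment without a culture should stay out of the main definition for three reasons: treating physicians know the arm (Protocol 13.6), the sponsor and study staff are unblinded after the 16-week analysis (SAP 13.4), and missing strain typing defaults to relapse.

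The cost is SAP wording. The 11.4 outcome and retreatment information are already collected, and no clinical procedure changes. The downside is that a few single-positive recurrences enter with less microbiological certainty, and some 11.4 conclusions may be reached after unblinding. The positive-culture requirement limits this, and the strict sensitivity analysis shows its effect.

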# 12.4 Treatment after End of Study Therapy (Post-study Access to Treatment)

The strategy recommended for participants to continue their TB treatment within the government health system is informed by two previous phase 2b TB trials with a 2-month experimental treatment, and the solution found for patients in Tanzania in collaboration with the national TB program in those past trials [27, 56, 59].

Patients who achieve two successive negative liquid media cultures, with no positives to follow by WK16 visit, the first of which is at or before WK 08, will NOT receive standard of care TB-treatment according to national guidelines as continuation phase to complete 6 months of treatment. Their planned post-treatment follow-up visits at WK 18, WK26, WK38 and WK52 will serve to determine

whether they have achieved lasting cure. Patients who will NOT fulfil at least one of these criteria will receive standard of care TB-treatment according to national guidelines until WK26 at a government health facility (continuation Phase).

They will be invited to return to the WK52 follow-up visit to determine their wellbeing and treatment outcome.

The review of culture results, and decision to discontinue or continue treatment will be made on the day before the WK16 visit. Should sufficient culture results to take this decision not be available by this timepoint, but available culture results indicate good response to treatment in the view of the investigator, this decision, and the start of continuation phase treatment, may be delayed until latest to WK16 (day112) + 6 days.

Should positive results become available after a decision is taken to discontinue treatment after WK16, the investigator should discuss these with the sponsor medical expert to come to a conclusion of whether the management of the patient should be changed, which should be done only in exceptions.

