5.2.2. Secondary Efficacy Endpoints

- Proportion of participants who suffer relapse, defined as recurrent disease caused by a strain indistinguishable to the baseline isolate (using whole genome sequencing), within 12 months post randomization, out of participants completing 16 weeks of therapy and achieving sustained sputum culture conversion defined as two successive negative liquid media cultures at or before WK08, with no positives to follow by the week 16 visit. Full definition of relapse in section 11.2.
- Time to recurrent TB, and to relapse, within 12 months post randomization.
- Time to culture conversion to negative on liquid media (defined as two negative cultures without an intervening positive culture).
- Proportion of participants converting to negative sputum culture in liquid media (defined as two negative cultures
 without an intervening positive culture) at each time point during treatment.
- Proportion of participants with negative sputum culture on solid media at WK 08 and other time-points.
- Proportion of participants developing drug resistance among those not converting to negative culture.

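### A participant who stops at week 16 and proves culture positive at WK16 is outside the relapse denominator in SAP 5.2.2 but inside it in SAP 11.2, and a positive pair starting at WK16 is not counted as relapse

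*SAP*

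**What the plan says.** - **Endpoint.** SAP 5.2.2, like Protocol 9.2.2, takes participants who complete 16 weeks and convert in liquid culture by week 08, "with no positives to follow by the week 16 visit. Full definition of relapse in section 11.2".
- **Classification.** SAP 11.2 opens by describing participants who complete therapy, convert early and terminate therapy. Its list of classes, however, removes only those not converted by week 8, on the ground that they do not end treatment at week 16. Relapse is "two consecutive culture positive timepoints without an intervening culture negative timepoint where the first occurs after Week 16 after randomization", timed by the analysis window, with a matching strain (missing or inconclusive typing counts as relapse). Anyone not otherwise classified is filed by culture status when last seen.
- **Conversion.** In SAP 11.4 the primary definition disregards positives that come after conversion. The second sensitivity definition lets a positive up to and including week 16 cancel conversion, and SAP 11.2 repeats the relapse analysis with it.
- **Windows.** SAP 12.6 sets Week 16 as Days 109-121 and Week 18 as Days 122-154. It adds that "These visit windows relate to analyses of tabulations of data by visit", yet SAP 11.2 invokes them for relapse.
- **Stop decision.** Protocol 12.4 places it on the day before the WK16 visit, with delay to at most Day 112 + 6 if results are insufficient. It has a provision beginning "Should positive results become available after a decision is taken to discontinue treatment after WK16": the case is discussed with the sponsor medical expert, and management changes only exceptionally.
- **Work-up.** Protocol 11.4 lists "A positive culture confirmed as M. tuberculosis from a sputum specimen collected at or after the WK16 visit" under the words "Triggers for the assessment will be the following events". The assessment then settles whether relapse is met, "conditional on a matching of baseline and recurrence isolate, if available".

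**The concern.** The WK16 sputum is collected after the scheduled stop decision. A participant who converted by week 08 can therefore stop treatment and later prove to have been positive on that day. This is direct evidence that stopping did not succeed for that participant, and the SAP calls relapse an important secondary outcome.

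The sections disagree on whether this participant belongs in the relapse analysis. Where the participant is kept, the positive at WK16 cannot serve as the first of the confirming pair. The Protocol synopsis and Protocol 11.4 send someone diagnosed with recurrence to the national programme for treatment. If that treatment works, later cultures are negative, and the relapse table shows a participant who was culture negative when last seen. A failure after stopping would then read like a success.

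**Working it through.** **1. The boundary.** From SAP 12.6, the first day after the Week 16 window is 121 + 1 = Day 122.
- WK16 visit: 112 ± 2 = Days 110-114, inside the Week 16 window.
- Latest delayed stop decision: 112 + 6 = Day 118, inside the Week 16 window.
- FU1: 126 ± 4 = Days 122-130, inside the Week 18 window.

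A WK16 specimen, or an unscheduled one up to Day 121, cannot start a qualifying pair. FU1 can.

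**2. One participant under each rule.** Converted by WK08, stopped at week 16, positive at WK16 and WK18, retreated, negative at WK26, WK38 and WK52.

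| Rule | In the relapse analysis? | Result |
|---|---|---|
| SAP 5.2.2 / Protocol 9.2.2 | No | Not counted |
| SAP 11.2, primary definition | Yes | Culture negative when last seen |
| SAP 11.2, second sensitivity definition | No | Not converted, hence presumed not to have ended treatment |
| Protocol 11.4 | Not a count | Work-up triggered; relapse only if the work-up and strain match support it |

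**3. How far the loss extends.** Take a week-08 converter who stopped and is positive at WK16. Assume all four follow-up visits are evaluable, one timepoint per window, same or untyped strain, no death. WK18, WK26, WK38 and WK52 give 2^4 = 16 patterns.
- Relapse under SAP 11.2 (a consecutive pair from WK18 on): ++++, +++-, ++-+, ++--, +-++, -+++, -++-, --++. That is 8 of 16.
- Relapse only if WK16 may start the pair: +-+-, +--+, +---. That is 3 of 16, for a total of 8 + 3 = 11. Two of the three end culture negative when last seen and one ends culture positive.
- No consecutive pair either way: -+-+, -+--, --+-, ---+, ----. That is 5 of 16.

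These are counts of patterns, not probabilities.

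**4. Size.** Let n be the stoppers in an arm and r its other relapses.
- Participant counted as a failure: (r + 1)/n.
- Participant filed by last culture: r/n.
- Difference: 1/n.

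With n at most the planned 15, 1/n is at least 1/15 = 6.7 points. With n = 10 (assumed) it is 10 points. If percentages are taken on the arm's full planned ITT number, it is again 1/15. If the participant is excluded instead, the rate is r/(n - 1). With r = 0 and n = 10, the three treatments give 1/10, 0/10 and 0/9.

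**5. An open point.** SAP 12.6 keeps one visit per window for by-visit analyses and does not say whether this applies to relapse. A work-up on Days 122-154 shares the Week 18 window with FU1. If visits collapse, two positives there are one timepoint. If they do not, they could already form a qualifying pair.

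**The case against.** Several counter-arguments have force.

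- **Protocol 11.4 is not a rival definition.** A reader might infer that the protocol counts relapse from any positive at or after WK16 while the SAP counts from Day 122. The text does not support this: the positive starts an assessment, which then decides.
- **Not every WK16-positive stopper is lost.** A reader might infer that none can be scored as relapse. Step 3 shows otherwise: WK18 and WK26 positive is a relapse under SAP 11.2. A work-up prompted by a late WK16 result may also yield specimens from Day 122 on.
- **Leaving the WK16 specimen out of relapse is defensible.** Treatment is scheduled through Day 112, so a WK16 positive can be read as persistence at end of treatment. No scheduled visit falls between Day 114 and Day 122.
- **Some handling already exists.** The primary SAP 11.2 analysis keeps these participants, Table 2.6 shows week 16 cultures by arm, and Table 2.10 has a row for culture positive when last seen.

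All of this stands, but the inconsistency remains. The two SAP sections still give different denominators. The sensitivity analysis removes participants for a reason that is untrue of them. Table 2.6 does not link a week 16 positive to having stopped, and the retreated participant in step 2 ends in the culture-negative row.

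**Conclusion.** The point holds in a limited form. SAP 5.2.2 and SAP 11.2 disagree on whether a WK16-positive stopper is in the denominator. A stopper whose only consecutive pair is WK16 and WK18 is classified by last culture in the primary analysis and dropped in the sensitivity analysis. No planned relapse count shows this participant as a failure after stopping.

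Each such participant moves an arm's rate by at least 6.7 points with the denominator held fixed, or 10 points if 10 stop. This rests on three assumptions: at most 15 stoppers per arm; the endpoint's cut-off at the week 16 visit includes the WK16 specimen (SAP 3.2.2 and 5.2.2 word it differently); and work-up specimens do not supply a separate qualifying pair.

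A reader might also infer that the understatement is worst in arms that clear bacilli slowly. The documents give neither the frequency of such participants nor any difference by arm, and slower arms may also have fewer stoppers. The relapse analysis is secondary and descriptive, so the consequence is a misleading table rather than a wrong test result.

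**What to change.** Reconcile Protocol 9.2.2 and 11.4 with SAP 5.2.2, 11.2 and 11.4 on this participant. In the SAP:

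1. Define the relapse denominator as participants who actually stopped treatment at week 16, in both the primary and the sensitivity analysis, whatever results arrive after the decision. This matches the opening sentence of SAP 11.2.
2. Report stoppers with a confirmed positive pair starting at the WK16 specimen, or at any specimen after the last dose up to Day 121, on a separate line within a combined count of relapse and failure after stopping. Relapse itself can keep its present start at Day 122; relabelling every WK16 positive as relapse is debatable and not needed.
3. State whether the one-visit-per-window rule applies to the relapse classification, and whether the endpoint's week 16 cut-off includes the WK16 specimen.

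The cost is SAP wording, one derivation from the last-dose date and one table row, with no new data. Aligning Protocol 9.2.2 formally would go through the amendment policy in Protocol 18.7. The reported rate may be slightly less favourable.
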